5.1 Patient Orientation

At the initial visit, patients are examined to determine whether they are eligible for the study and if so the study is discussed with them. They are informed of the possible risks and benefits of the study treatment. The patient's likely eligibility is assessed. The patient either reads the detailed informed consent or it is read to them and the patient is given time to study the patient information sheet. Any questions related to the study will be answered. The patient is allowed some time to consider the study prior to the consent form being signed.

5.2 Baseline Examination (Screening Visit)

If the patient is willing and has agreed to participate in the study then a complete baseline examination is conducted (does not need to be the same day as the signing of the consent) which includes the following

- a) Visual Acuity. Best corrected visual acuity will be assessed on LogMAR chart
- b) Intraocular Pressure (IOP) measurement
- c) Slit lamp examination for grading of lens opacities
SD OCT: High definition Spectral domain Volume Scan or Macula Cube
Cross Hair scan or HD 5-line raster
- d) Fundus photography and fluorescein angiography. See Section 12 for photography and angiography details.
- e) Fundus autofluorescence. See Section 13.1
- f) Urine pregnancy test (for women of child bearing potential only)
- g) Blood pressure
- h) Assessment of concomitant medications and medical history
- i) Visual function as assessed by Microperimetry

Full baseline assessment will be performed on the Tuesday or Friday on the week immediately prior to starting NIR treatment. If clinics/staff are not available for baseline assessment on Tuesday or Friday, another day in the week immediately prior to starting NIR treatment may be selected, however the remaining treatment and visit schedule must be adhered to according to the protocol.

5.3 Day 1

Once the patient has met all of the eligibility criteria they will return for the Day 1 visit which will occur on the Wednesday the week after screening. The following procedures will occur at this visit:

- a) AE and Conmed history
- b) Microperimetry
- c) Dilation of study eye
- d) Confirmation of eligibility
- e) NIR light treatment

6 NIR Light Treatment

NIR light treatment will commence on the Wednesday of the next week after the baseline visit.

The procedure will be performed whilst the participant is seated at a slit lamp according to the set protocol:

The patient will be seated at the slit lamp laser delivery system and after the eye has been dilated and anaesthetised with topical eye drops a standard fundus contact lens (area centralis) will be placed on the eye through which the posterior pole will be visualised while the treatment is delivered.

Each NIR light treatment will consist of a 90 second exposure of the macula of the study eye to the ELLEX Integre NIR laser with the patient fixating on the central aiming beam. The laser light beam is 4.5mm in diameter with a central masked area of 1.0 mm diameter containing the central fixation target. In this way the central macula will be spared in the event of an adverse effect of the laser, which we do not anticipate.

6.1 Treatment Week 1

Treatment 1 will be applied on Wednesday and Treatment 2 on Friday.

6.2 Treatment Weeks 2-4

Treatments 2 to 11 will be applied on the Monday, Wednesday and Friday of each subsequent week for 3 weeks.

6.3 Treatment Week 5

On week 5 patients will have their final laser treatment (12) on Monday and will be assessed on the Tuesday.

The investigator can use clinical discretion to determine if the patient would not benefit from receiving further treatment at any time point during the treatment schedule or if any adverse events appear to occur.

6.4 Rescue Treatment & Standard of Care

Patients with an increase of 100 microns in central macular thickness on OCT or a significant loss of vision (defined as a loss of 10 or more letters [2 lines] on a vision chart) at any stage in the study will

be discontinued from the study treatment and treated as per standard of care. Patients who are discontinued from the study and are treated with the standard of care during the study period will continue to be followed for the safety at the specified time points.

At the 16 week visit, patients will be assessed for the need for standard of care therapy according to each investigator's usual practice.

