Patients with diabetic macular oedema in one eye as defined by the eligibility criteria will receive thrice weekly 90 second treatments with NIR laser, supplied by Ellex, for 4 weeks. Twenty one patients will be sequentially allocated into three groups to receive laser doses 25, 100 or 200 mW/cm². The central 1 mm will be shielded so that the fovea will be protected in the event of any unanticipated toxic effect on the retina.

1.3.1 Primary outcome:

- Reduction in central macular thickness measured by optical coherence tomography at the conclusion of treatment and at 8 weeks compared with baseline.

1.3.2 Secondary outcomes:

- LogMAR Best Corrected Visual Acuity (BCVA)
- Time to oedema reduction
- Time to oedema recurrence
- FFA assessment of leak and capillary closure before (at baseline) and after intervention (week 5 and 16)
- Change in retinal sensitivity (dB) as measured by microperimetry from Baseline to Week 1, Week 5, Week 16 and 6 month follow up visit.

1.4 Power calculation:

This study is an exploratory study designed to provide estimates of outcomes for future studies, therefore power calculations have not been applied. Seven patients per group will be sufficient to produce these estimates and will give an indication of the effective dose range

1.5 Significance:

This study will shed light on whether a novel treatment that may complement existing treatments is safe and whether it warrants further investigation in a larger study

2 Research Plan

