2.2.2 Secondary Outcome measures at 1month, 8 weeks, 12 weeks and 16 weeks

- Best corrected LogMAR Visual Acuity (VA)
- Time to oedema reduction
- Time to oedema recurrence
- FFA assessment of leak and area of ischemia before and after intervention
- Change in retinal sensitivity (dB) as measured by microperimetry from Baseline to Week 5, 8, Week 16 and 6 month visit.

2.2.3 Safety outcomes will be:

- Any loss of VA
- Any increase in macular thickness as measured by OCT

3 Design

A cohort of 21 patients satisfying the inclusion criteria will be recruited from the outpatient hospital clinic. They will be sequentially allocated into one of three groups. Each group will have seven patients with group 1 enrolment completed first, followed by group 2 and finally, group 3. Each group will be managed identically but will receive a different dose of NIR energy.

Group 1 will be treated with a dose of 25 mW/cm² for 90 seconds (now fully enrolled)

Group 2 will be treated with a dose of 100 mW/cm² for 90 seconds (now fully enrolled)

Group 3 will be treated with a dose of 200 mW/cm² for 90 seconds.

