7.2.1 Safety follow-up visit

There is a safety follow-up visit 6 months after the last administration of study laser treatment. If a patient has withdrawn early from the study they will still be asked to attend these visits.

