8.1 Primary and Secondary Outcomes

Primary outcome:

- Reduction in high definition Spectral Domain Heidelberg Optical Coherence Tomography (OCT) subfield volume measurements at 8 weeks.

Secondary outcomes at 1 and 2 months:

- LogMAR VA
- Time to fluid reduction
- Time to oedema recurrence
- FFA assessment of leak and capillary closure before (at baseline) and after intervention (Week 5 and 16)
- Change in retinal sensitivity (dB) as measured by microperimetry from Baseline to week 1, week 5, week 8 and Week 16

Safety outcomes will be:

- Any loss of BCVA/VA
- Any increase in any OCT subfield

9 Statistical aspects of the study, safety and reporting

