9.3 Safety monitoring

The incidence of adverse events will be recorded throughout the duration of the study and at the safety follow up visits. The trial will be stopped if there is a significant ($P = 0.01$) incidence of severe adverse events or any event arises which renders continuation of the study not to be in the interests of participants.

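### Sections 1.3.2 and 2.2.2 carry the microperimetry outcome to 6 months, about 15 weeks after the Week 16 standard-of-care assessment, whereas Section 8.1 ends it at Week 16

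*Protocol*

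**What the plan says.** Section 6.4 has two routes to standard of care. One is the rescue rule, triggered by a thickness or letter-loss threshold at any stage. The other is tied to a visit and has no protocol threshold: "At the 16 week visit, patients will be assessed for the need for standard of care therapy according to each investigator's usual practice". Section 2.1 describes intravitreal VEGF inhibitors and glucocorticoids as first-line treatment for this condition.

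The microperimetry outcome appears in three lists that do not agree:

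- Section 1.3.2: "Change in retinal sensitivity (dB) as measured by microperimetry from Baseline to Week 1, Week 5, Week 16 and 6 month follow up visit".
- Section 2.2.2: "Change in retinal sensitivity (dB) as measured by microperimetry from Baseline to Week 5, 8, Week 16 and 6 month visit". The heading of that section gives its time points as 1 month and 8, 12 and 16 weeks.
- Section 8.1: "microperimetry from Baseline to week 1, week 5, week 8 and Week 16", with no 6-month entry.

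On the late visit, Section 7.2.1 says: "There is a safety follow-up visit 6 months after the last administration of study laser treatment". Section 2.2 and the visit table in Section 15 also label it a safety visit. The table schedules microperimetry, VA, BCVA and OCT there, and records concomitant medications and procedures.

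**The concern.** An outcome listed beside visual acuity and oedema recurrence will be read as a measure of what NIR did. By 6 months some eyes may have received an effective non-study treatment, chosen at Week 16 by the individual investigator. Eyes that are still swollen at Week 16 are the likeliest to be treated, so the extra treatment would go mainly to eyes in which NIR had done least.

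Two features of this trial make that matter. Section 2.1 reports that first-cohort results hint at a delayed benefit after NIR ends, so a late gain in sensitivity is what a reader will look for, and standard of care could produce one. Section 1.4 also says the study should indicate the effective dose range. If a less effective dose leaves more eyes needing treatment, later treatment would tend to flatten the contrast between doses at 6 months.

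**Working it through.** The protocol states no figure for this point, so there is none to reproduce. The check sets the texts side by side and adds calendar arithmetic.

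**1. Time points for microperimetry**

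| Place | Wk 1 | Wk 5 | Wk 8 | Wk 16 | 6 months |
|---|---|---|---|---|---|
| 1.3.2 | yes | yes | no | yes | yes |
| 2.2.2 | no | yes | yes | yes | yes |
| 8.1 | yes | yes | yes | yes | no |
| Visit table, Section 15 | yes | yes | yes | yes | yes |

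Two of the three outcome lists include 6 months. The visit table shows that the measurement is taken then, but it does not make it an efficacy outcome. Section 8.1 has a loose end of its own: its heading speaks of 1 and 2 months, while the microperimetry item runs to Week 16.

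**2. Gap between the Week 16 assessment and the 6-month visit**

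Inputs: first laser on Wednesday of Week 1 (Section 6.1), last laser on Monday of Week 5 (Section 6.3), safety visit 6 months after the last laser (Section 7.2.1), windows of ±1 week at Week 16 and ±2 weeks at 6 months (Section 15).

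- Take Wednesday of Week 1 as day 0. The last laser is then day 26, and Week 16 is day 15 × 7 = 105.
- The 6-month visit is day 26 + 26 × 7 = 208.
- Gap = 208 − 105 = 103 days = 14.7 weeks. Counting by week labels instead, 5 + 26.1 − 16 = 15.1 weeks. Either way it is about 15 weeks.
- The windows add or remove up to 1 + 2 = 3 weeks, giving about 12 to 18 weeks.
- As a share of the post-laser period, 103 / 182 = 57%. This is elapsed time, not a measure of bias.

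**3. Is that gap short enough for Week 16 treatment to matter at 6 months?**

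The exclusion criteria in Section 4.2.2 give the protocol's own look-back periods: 4 months for retinal laser, 6 months for intravitreal triamcinolone and 2 months for anti-VEGF drugs. The nominal gap is 15.1 / 4.345 = 3.5 months.

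- Laser or triamcinolone given at Week 16 would still be inside its look-back at the nominal 6-month visit.
- At the widest window (18.1 / 4.345 = 4.2 months), laser would fall just outside and triamcinolone would stay inside.
- Anti-VEGF would be inside its look-back if given in the last 2 months before the visit.

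**4. How many eyes?**

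The documents give no uptake rate. With 7 per group (Section 3), one treated eye has weight 1/7 = 14% in its group mean. Purely as an assumption, let each patient start standard of care at Week 16 with probability p. The chance that a group has at least one such eye is 1 − (1 − p)^7:

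| Assumed p | Chance of at least one in 7 | Expected number in 7 |
|---|---|---|
| 10% | 52% | 0.7 |
| 30% | 92% | 2.1 |
| 50% | 99% | 3.5 |

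Even modest uptake would make an unmixed dose group at 6 months uncertain. The table says nothing about the size of the resulting shift, which would also need a treatment effect in dB that the documents do not supply.

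**The case against.** The strongest reply is that the protocol already contains the answer. Its Endpoints section stops microperimetry at Week 16, the heading of 2.2.2 stops at 16 weeks, and the 6-month visit is called a safety visit wherever it is described. On this view the 6-month entries are a drafting inconsistency, and no text claims a durable effect. That largely stands, and it is why the remedy is to reconcile the lists. It does not remove the point: two of the three lists, including the synopsis, still make the 6-month change an outcome.

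It may also be said that data after non-study therapy are a matter for the statistical analysis plan, which is not at hand. That is fair for the handling rule, and no missing rule is alleged here. Where the outcome's time points end is fixed by the protocol.

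Three stronger readings may tempt a reader, and the documents do not support them:

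- *Everyone goes on to standard of care at Week 16.* Section 6.4 says only that need is assessed. Nor is Week 16 where mixing first becomes possible, since rescue can occur at any stage.
- *Late harm will be hidden.* The safety outcomes are any loss of VA and, in Section 2.2.3, "Any increase in macular thickness as measured by OCT". They are per-patient events with no stated 6-month time point, and an event recorded by Week 16 is not erased by later care. Adverse events are collected through the safety visit (Section 9.3: "The incidence of adverse events will be recorded throughout the duration of the study and at the safety follow up visits"). Treatment could prevent or mask a change that would first appear after Week 16, but that follows from giving care and is not an error in the plan.
- *The 6-month mean is biased by a known number of dB.* Neither the uptake nor the effect is in the documents, so any such figure would be wholly assumed.

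**Conclusion.** The point holds for one outcome at one visit. Sections 1.3.2 and 2.2.2 place a retinal sensitivity outcome about 15 weeks (12 to 18) after patients are assessed for standard of care, and this contradicts Section 8.1, the heading of 2.2.2 and the safety label of the visit. The trial has no untreated group and no masking, so a 6-month change in an eye that has started standard of care cannot be attributed to NIR. The same applies to eyes rescued earlier under Section 6.4.

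The conclusion requires only that some eyes start standard of care by the 6-month visit. Their share, and hence the size of any distortion, is unknown. A reader might infer that the primary result is compromised; the Week 16 rule comes after the 8-week primary outcome and does not touch it. This is worth correcting because the correction is cheap, but it is confined to a secondary outcome in an exploratory study.

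**What to change.** - In Sections 1.3.2 and 2.2.2, end the microperimetry efficacy outcome at Week 16, as in Section 8.1. Align the earlier weeks in the three lists at the same time.
- Keep microperimetry, VA and OCT at 6 months as safety follow-up. Describe them by whether standard of care had been started by then, using the concomitant medication and procedure records already scheduled. With seven per group these subsets will be very small and selected on response, so the split is descriptive and not a comparison.
- State that no NIR efficacy or durability conclusion will be drawn from pooled 6-month values.

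The cost is protocol wording and one split in a table, with no added visit or procedure. The downside is giving up a 6-month efficacy reading for sensitivity. No change to rescue, to care at Week 16 or to any other clinical rule is proposed.

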6.5 Assessments

VA and OCT will be performed on the Friday of each treatment week.

The full final assessment will be performed on Tuesday following Treatment 12.

7 Patient Visits and Examination

7.1 Introduction

Patients will be assessed with respect to safety outcomes for which standardised procedures have been developed:

- BCVA/VA by a trained technician will be undertaken.
- Adverse events assessment
- Concomitant Procedure assessment
- Dilated fundal examination
- Grading of cataract and anterior and posterior chamber cells
- Macular thickness by optical coherence tomography (OCT)
- Visual function as assessed by Microperimetry

Refer to the Schedule of Visits table in Section 15 regarding the timing for each of these assessments

7.2 Patient follow-up

Patients will be seen for treatment visits according to Section 6 above and then for an assessment visit at week 8.

The schedule of visits table in Section 15 outlines the timing for each of the required assessments.

Any patient missing an appointment will be contacted within 1 day to establish their status and another appointment will be made immediately.

In the event that a patient withdraws from the study, an early exit visit should be conducted where possible.

7.2.1 Safety follow-up visit

There is a safety follow-up visit 6 months after the last administration of study laser treatment. If a patient has withdrawn early from the study they will still be asked to attend these visits.

7.3 Treatment of Adverse events

7.3.1 Introduction

Adverse Event Definition: Any undesirable clinical occurrence in a subject whether it is considered to be device related or not, that includes a clinical sign, symptom or condition and/or an observation of an unintended technical performance or performance outcome of the device.

Examples of an AE **include**:

- Exacerbation of a chronic or intermittent pre-existing condition including either an increase in frequency and/or intensity of the condition.
- New conditions detected or diagnosed after investigational treatment administration.
- Signs, symptoms, or the clinical sequelae of a suspected interaction.
- Signs, symptoms, or the clinical sequelae of a suspected overdose of a concurrent medication (overdose per se should not be reported as an AE/SAE).

This trial is being carried out in the facilities of quaternary ophthalmic referral centre with extensive experience in laser therapy. The medical staff are well experienced in dealing with all adverse events associated with laser therapy.

Adverse events will be collected from the first NIR laser treatment visit, not necessarily from the date of consent in the event that the patient is not treated on the same day as they are consented. The incidence of adverse events will otherwise be recorded throughout the duration of the study and at the safety follow up visit. These will be graded by the Principal Investigator as mild, moderate or severe.

Serious Adverse Event Definition: Any untoward medical occurrence that:

- results in death;
- is life-threatening;
- requires inpatient hospitalization or prolongation of existing hospitalization;
- results in persistent or significant disability/incapacity; or
- is a congenital anomaly/birth defect

For SAE's the relationship to study treatment will be graded as related, unrelated, probable, unlikely or likely. SAE's will also be graded as expected or unexpected

Serious adverse events (SAE's) as defined by the International Conference on Harmonisation, Good Clinical Practice (ICH-GCP) as per above will be reported as SAE's to the approving HREC according to local requirements.

The following events are to be considered adverse events but not serious adverse events and therefore reporting as SAE's is not required:

- Hospitalizations for elective surgery
- Hospitalizations for admissions of less than 24 hours in duration
- Hospitalizations to the emergency department not requiring admission within the hospital
- Care delivered as "hospital in the home" or similar in home service (unless other SAE criteria are met such as persistent disability)

Pregnancies are not considered AE's or SAE's, however pregnancies in female study patients will be recorded in the study data.

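### Section 7.3.1 contradicts itself on serious adverse events: the short-stay and emergency department exemptions lack the proviso that keeps the other SAE criteria in force

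*Protocol*

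**What the plan says.** All the text at issue is in Protocol Section 7.3.1.

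- **Definition.** An SAE is an event meeting any one of five criteria. Three matter here: it "results in death", it "is life-threatening", or it "requires inpatient hospitalization or prolongation of existing hospitalization".
- **Duty to report.** SAEs defined in this way, which the protocol attributes to ICH-GCP, "as per above will be reported as SAE's to the approving HREC according to local requirements".
- **Exemption list.** The list is introduced by "The following events are to be considered adverse events but not serious adverse events and therefore reporting as SAE's is not required". Four items follow: hospital stays for elective surgery; "Hospitalizations for admissions of less than 24 hours in duration"; "Hospitalizations to the emergency department not requiring admission within the hospital"; and hospital-type care given at home.
- **Proviso.** Only the home-care item carries the qualification "unless other SAE criteria are met such as persistent disability".

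Section 7.3.3 requires every adverse event, serious or not, to be entered in the eCRF with dates, action taken, outcome, intensity and causality. Section 11.2 makes the Principal Investigator or a nominee responsible for prompt reporting of SAEs to the HREC. Section 9.3 bases the stopping rule on severe adverse events, or on any event that makes continuing contrary to participants' interests.

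**The concern.** The definition and the list give opposite answers for the same event. Whether an event threatens life does not depend on the place or length of treatment, and the definition respects that. The list classifies by place and length of treatment, and for three of its items says nothing about events that are serious on another ground.

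The case can arise in this trial. Fluorescein is injected at Week 5 and Week 16 (Sections 12.3 and 15), both after adverse event collection starts at the first laser treatment. The protocol recognises the hazard by excluding patients with known fluorescein allergy (Section 4.2.2). An acute reaction of this kind may well be treated in an emergency department or in a stay of less than a day.

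At stake is whether the HREC is told of such an event as an SAE, and whether it is graded expected or unexpected, a grading that Section 7.3.1 specifies only for SAEs. Groups are enrolled in sequence at rising dose, seven patients each, so one misclassified event would matter to the safety picture of a group.

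**Working it through.** No arithmetic applies beyond a count of items. The check sets the definition against the list and runs test cases through both.

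**Step 1: does the definition limit setting or duration?** No. Death and threat to life stand alone. The hospitalization criterion requires inpatient care but sets no minimum stay.

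**Step 2: does the introduction to the list limit its effect?** No. It declares the listed events not serious. It does not say that they are non-serious only as regards hospitalization.

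**Step 3: which items keep the other criteria?**

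| Exempt item | Proviso attached? |
|---|---|
| Elective surgery | No |
| Admission under 24 hours | No |
| Emergency department, not admitted | No |
| Hospital-type care at home | Yes |

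One of four items keeps the other criteria; three of four do not.

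**Step 4: test cases.**

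| Event | By the definition | By the list, read literally |
|---|---|---|
| Life-threatening, treated in the emergency department, not admitted | SAE (threat to life) | Not an SAE |
| Life-threatening, admitted for under 24 hours | SAE (threat to life; inpatient stay) | Not an SAE |
| Fatal within 24 hours of admission | SAE (death; inpatient stay) | Not an SAE |
| Not life-threatening, admitted for under 24 hours | SAE (inpatient stay only) | Not an SAE |
| Not life-threatening, emergency department only, no other criterion met | Not an SAE | Not an SAE |
| Life-threatening, treated at home | SAE | SAE, because the proviso applies |

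The first three rows are the conflict that matters. The fourth is also a mismatch, but can be understood as a deliberate narrowing of the hospitalization criterion. The last two agree.

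**Step 5: does any other text decide between them?** No precedence rule is stated. The HREC duty in Section 11.2 and the commitment to ICH GCP in Section 11.1 concern events already classified as SAEs, so they depend on the classification in dispute.

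**Step 6: what depends on the answer?** Three things do: the SAE label, the expected/unexpected grade, and SAE reporting to the HREC. Two do not: the eCRF record (Section 7.3.3) and the stopping rule (Section 9.3), which refers to severity and to participants' interests.

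**The case against.** The best defence is that the list narrows the hospitalization criterion and nothing else. The first three items are worded as hospitalizations, so what loses its serious status is the hospital stay, while death and threat to life remain criteria of their own. The home-care item is worded as care rather than as hospitalization, which may be why it alone has a proviso. Sections 11.1 and 11.2 also lean toward reporting.

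This reading is possible, and the authors may have meant it. It does not remove the conflict, for three reasons. The introduction to the list is unqualified. A proviso on one item invites the inference that it is absent by design from the others. And attendance without admission would not meet the inpatient criterion anyway, so the emergency department item is either redundant or removes events that qualify on another ground.

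The objection does stand against several stronger readings that a reader might infer:

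- *That the list overrides the definition, so these events are exempt.* The protocol does not say so. It leaves two statements unreconciled.
- *That the chief danger is unreported deaths.* The formal conflict covers them, but a death is the event least likely to be read as a mere short hospitalization. The life-threatening case is the core.
- *That the elective surgery item is wrong in itself.* Planned surgery would usually touch only the hospitalization criterion. Whether to limit the item to surgery planned before the study is a convention about scope that this document does not settle.
- *That safety data would be lost or the stopping rule disabled.* Sections 7.3.3 and 9.3 do not support this.
- *That the number of laser sessions or angiograms measures the problem.* Those counts measure exposure to procedures, not events affected by the wording.

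**Conclusion.** The point holds as an internal contradiction in the rule that triggers SAE reporting. For a life-threatening event managed in the emergency department without admission, or in a stay under 24 hours, Section 7.3.1 gives two incompatible classifications, and a site following the list literally could omit the SAE report. A fatal event falls under the same wording, less plausibly.

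Its size is textual: three of four exempt items lack the proviso. The documents give no rate for such events, so none is estimated. The practical consequence is limited to SAE classification, the expected/unexpected grade and HREC reporting. The primary outcome and its analysis are not touched. The conclusion assumes that a site would apply the list as written; a site that reads it as narrowing only the hospitalization criterion would still report. That two careful sites could differ is reason enough to correct the text.

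**What to change.** Reconcile the definition and the list in Section 7.3.1 by moving the existing proviso from the home-care item to the introductory sentence, so that it governs all four items. Suggested wording: *The following are not SAEs solely by reason of hospitalization or care setting, unless any other SAE criterion is met.* The four items can then stay as they are, without the proviso on the last.

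With this change the first three test cases become SAEs under both parts of the section. The short, non-life-threatening admission becomes a stated exception to the hospitalization criterion instead of a contradiction of it.

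The cost is an amendment of a sentence or so, with HREC approval under Section 11.3 if it is treated as bearing on patient safety, and possibly a few more SAE reports. No visit, measurement or analysis changes.
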